10.4.2 General guidelines for reporting adverse events

- All AEs, regardless of seriousness or relationship to IMP/NIMP, spanning from the signature of the informed consent form until the end of the study as defined by the protocol for that patient, are to be recorded on the corresponding page(s) or screen(s) of the e-CRF.
- Whenever possible, diagnosis or single syndrome should be reported instead of symptoms. The Investigator should specify the date of onset, intensity, action taken with respect to IMP, corrective treatment/therapy given, additional investigations performed, outcome, and his/her opinion as to whether there is a reasonable possibility that the AE was caused by the IMP or by the study procedure(s).
- The Investigator should take appropriate measures to follow all AEs until clinical recovery is complete and laboratory results have returned to normal, or until progression has been stabilized, or until death, in order to ensure the safety of the patients. This may imply that observations will continue beyond the last planned visit per protocol, and that additional investigations may be requested by the monitoring team up to as noticed by the Sponsor. Patients who experience an ongoing SAE or an AESI, at the prespecified study end-date, should be followed until resolution, stabilization, or death and related data will be collected.
- When treatment is prematurely discontinued, the patient, at a minimum, should then be followed-up for 4 Weeks from the last administration of IMP or until recovery or stabilization of any AE as specified in this protocol, whichever comes last. A final end of study visit will take place 4 weeks after the premature discontinuation.

- Laboratory and vital signs abnormalities are to be recorded as AEs only if:
 - Symptomatic and/or
 - Requiring either corrective treatment or consultation, and/or
 - Leading to IMP discontinuation or modification of dosing, and/or
 - Fulfilling a seriousness criterion, and/or
 - Defined as an AESI

Instructions for AE reporting are summarized in [Table 9](#).

10.4.3 Instructions for reporting serious adverse events

In the case of occurrence of an SAE, the Investigator or any designees must immediately:

- ENTER (within 24 hours) the information related to the SAE in the appropriate screens of the e-CRF; the system will automatically send a notification to the monitoring team after approval of the Investigator within the e-CRF or after a standard delay.
- SEND (preferably by fax or e-mail) a photocopy of all examinations carried out and the dates on which these examinations were performed, to the representative of the monitoring team whose name, fax number, and email address appear on the clinical trial protocol. Care should be taken to ensure that the patient's identity is protected and the patient's identifiers in the clinical trial are properly mentioned on any copy of a source document provided to the Sponsor. For laboratory results, include the laboratory normal ranges.
- All further data updates should be recorded in the e-CRF as appropriate, and further documentation as well as additional information (for laboratory data, concomitant medications, patient status, etc) should be sent (by fax or e-mail) to the monitoring team within 24 hours of knowledge of the SAE. In addition, every effort should be made to further document any SAE that is fatal or life-threatening within a week (7 days) of the initial notification.
- A back-up plan (using a paper CRF process) is available and should be used when the e-CRF system does not work. If the e-CRF system does not work, the investigator must report an SAE to the Sanofi representative within 24 hours, and the Sanofi representative must report the SAE to Global Pharmacovigilance & Epidemiology (GPE) within 1 working day.

Any SAE brought to the attention of the Investigator at any time after the end of the study for the patient and considered by him/her to be caused by the IMP with a reasonable possibility, should be reported to the monitoring team.

10.4.4 Guidelines for reporting adverse events of special interest

For AESIs, the Sponsor must be informed immediately (ie, within 24 hours), as per SAE notification guidelines described in [Section 10.4.3](#), even if not fulfilling a seriousness criterion, using the corresponding pages of the CRF (to be sent) or screens in the e-CRF.

Instructions for AE reporting are summarized in [Table 9](#).

Table 9 - Summary of adverse event reporting instructions

Event category	Reporting timeframe	Specific events in this category	Case Report Form completion		
			AE form	Safety Complementary Form	Other specific forms
Adverse Event (non-SAE, non-AESI)	Routine	Any AE that is not SAE or AESI	Yes	No	No
Serious Adverse Event (non-AESI or AESI)	Expedited (within 24 hours)	Any AE meeting seriousness criterion per Section 10.4.1.2	Yes	Yes	No
Adverse Event of Special Interest	Expedited (within 24 hours)	Acute hypersensitivity/ anaphylaxis	Yes	Yes	No
		Pregnancy	Yes	Yes	Yes
		Symptomatic overdose	Yes	Yes	No
		ALT increase as defined in the protocol	Yes	Yes	Yes
		General allergic event requiring consultation with another physician	Yes	Yes	Yes
		Local injection site reactions requiring consultation with another physician	Yes	Yes	Yes
		Neurologic events that require additional examinations/procedures and/or referral to a specialist	Yes	Yes	Yes
Neurocognitive events (any)	Yes	Yes	Yes		

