9.2.5 Safety assessments

Adverse events, spontaneously reported by the subject or observed by the Investigator, will be monitored at each visit. This includes SAEs, detailed in [Section 10.4.1.2](#), AEs of special interest (AESIs) detailed in [Section 10.4.1.3](#), laboratory data, vital signs assessed throughout the study. Specific additional forms will be completed for AESI. For any Local Injection Site Reactions (LISR), and general allergic AEs, whether or not reported as AESI, special forms on symptoms will have to be completed (see [Section 10.6](#)).

Assessment of safety will be based on clinical safety endpoints, laboratory safety variables, vital signs, and physical examination.

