 - Any general allergic events regardless of the cause that require consultation with another physician for further evaluation of hypersensitivity/allergy as per the Investigator's medical judgment should be reported as an AESI.
 - All general allergic events require completion of the specific e-CRF screen.

- **Local injection site reactions:**

- Local injection site reactions that require consultation with another physician for further evaluation of hypersensitivity/allergy as per the Investigator's medical judgment should be reported as an AESI.

All LISR require completion of the specific e-CRF screen.

Note:

- Other LISR are non-AESIs. Please see [Section 10.6](#) for details.
 - The safety instructions on allergic events and LISR are detailed in [Section 10.6](#).
- **Neurologic events:** neurologic events that require additional examinations/procedures and/or referral to a specialist should be reported as an AESI. If the event does not require additional examinations/procedures and/or referral to a specialist, it should be reported as a standard AE.
 - **Neurocognitive events:** All neurocognitive events will be considered as AESI.

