10.6.2.2 Acute allergic injection reactions

Acute allergic injection reaction (which are considered under the category of general allergic events) is defined as any AE that occurs during or shortly after injection of the IMP (characterized by but not limited to hypotension, bronchoconstriction, urticaria, edema, angioedema, nausea, vomiting). Emergency equipment and medication for the treatment of these potential adverse effects (eg, antihistamines, bronchodilators, IV saline, corticosteroids, acetaminophen, and epinephrine) must be available for immediate use for the injections at the training, and inclusion visits. Patients will be observed at the investigational site for at least 30 minutes following the injection that takes place at the inclusion visit. Patients should be treated symptomatically if any AEs are observed. Patients are to remain at the site until any acute injection reaction is assessed as stable, per the Investigator's discretion.

A General Allergic Event and/or Local Injection Site Reaction Complementary Form will have to be completed.

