2.1.4.5.1 Adverse events variables

Adverse events (including SAEs and AESIs) are recorded from the time of signed informed consent until the end of study.

All AEs will be coded to a “lowest level term”, “PT”, “HLT”, “HLGT”, and associated primary “SOC” using the version of MedDRA currently in effect at Sanofi at the time of database lock.

Adverse event observation period

- Pre-treatment AEs are AEs that developed or worsened or became serious during the pretreatment period.
- Treatment-emergent adverse events are AEs that developed or worsened or became serious during the TEAE period.
- Post-treatment AEs are AEs that developed or worsened or became serious during the post-treatment period.

Adverse events of special interest

AESIs are AEs (serious or non-serious) that need to be monitored, documented, and managed in a pre-specified manner described in the protocol. In this study, AESI are the following (their complete descriptions are provided in the protocol):

- Local injection site reactions, selected using e-CRF specific tick box on the AE page;
- Allergic events:
 - General allergic events will be tabulated. Events will be selected using standardized MedDRA query (SMQ) “hypersensitivity” (broad and narrow) excluding the following PTs linked to local injection site reactions (“infusion site dermatitis”, “infusion site hypersensitivity”, “infusion site rash”, “infusion site urticaria”, “injection site dermatitis”, “injection site hypersensitivity”, “injection site rash”, “injection site urticaria” and “injection site vasculitis”);
 - General allergic events and local allergic reactions at IMP injection site will be described. This selection will be based on the above selection for general allergic event and on the following selection of PT from the symptoms complementary form for local injection site reaction ("Injection site dermatitis", "Injection site hypersensitivity", "Injection site oedema", "Injection site rash", "Injection site urticaria", "Injection site eczema", "Injection site vasculitis", "Injection site swelling", "Infusion site dermatitis", "Infusion site hypersensitivity", "Infusion site oedema", "Infusion site rash", "Infusion site urticaria", "Infusion site swelling")
- ALT ≥ 3 ULN (if baseline ALT < ULN) or ALT ≥ 2 times the baseline value (if baseline ALT \geq ULN), selected using laboratory data

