 - TEAE leading to permanent treatment discontinuation
- All TEAEs by primary SOC, HLG, HLT, and PT
- All TEAEs by primary SOC and PT
- All TEAEs by treatment group regardless of relationship in one column and, in the same table a second column with TEAEs related to alirocumab according to investigator's opinion by primary SOC, HLG, HLT and PT
- All TEAEs by maximal intensity (ie, mild, moderate or severe), presented by primary SOC and PT

Analysis of all treatment emergent serious adverse event(s)

- All serious TEAEs by primary SOC, HLGT, HLT, and PT and by SOC/PT
- All serious TEAEs by treatment group regardless of relationship in one column and, in the same table a second column with TEAEs related to alirocumab according to investigator's opinion, by primary SOC, HLGT, HLT, and PT

Analysis of all treatment-emergent adverse event(s) leading to treatment discontinuation

- All TEAEs leading to treatment discontinuation, by primary SOC, HLGT, HLT, and PT and by SOC/PT

Analysis of groupings of adverse events including selected adverse events of special interest:

- All grouping of TEAEs including AESI as listed in [Section 2.1.4.5.1](#) will be analyzed using selections defined in [Section 2.1.4.5.1](#) and will be presented by SMQ/CMQ and PT (when selection is based on SMQs/CMQs) and by SOC and PT (when selection is based on the e-CRF tick box or HLGT/HLT). The summaries will be sorted by decreasing incidence of PT within each SOC/SMQ (in the SYDNEY group for tables performed on the parallel-arm period)

In addition, the following variables will be tabulated for the local injection site reactions TEAEs:

- Intensity of the event (mild, moderate, severe)
- Number of events divided by the number of IMP injections received
- Time from first IMP injection to first injection site reaction
- Description of the highest intensity of each symptom recorded in the specific e-CRF page

Analysis of TEAE(s) linked to PTC:

- All TEAEs related to PTC by primary SOC, HLGT, HLT, and PT

Analysis of pre-treatment and post-treatment adverse events

- All pre-treatment AEs by primary SOC and PT
- All pre-treatment AEs leading to treatment discontinuation by primary SOC and PT
- All post-treatment AEs by primary SOC and PT
- All post-treatment SAE by primary SOC and PT

2.4.4.2.5.2 Deaths

The following summaries of deaths will be generated.

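### Protocol Table 9 asks for no specific form for non-serious, non-AESI events, contradicting the rule for injection-site and general allergic reactions; two SAP outputs could lose data

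*Protocol*

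**What the plan says.** Protocol Sections 10.4.2 and 10.4.4 both send sites to Table 9 for a summary of adverse event reporting. Its first row covers "Any AE that is not SAE or AESI". The entries are AE form Yes, Safety Complementary Form No, other specific forms No. The row has no exception or footnote.

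The protocol text sets a different rule for two kinds of event. Section 10.4.1.3 says "All LISR require completion of the specific e-CRF screen" and applies the same requirement to general allergic events. It also classes an LISR as an AESI only when another physician has to be consulted; all other LISRs are non-AESI. Section 9.2.5 says of both event types that "whether or not reported as AESI, special forms on symptoms will have to be completed". Sections 10.6.1 and 10.6.2 ask for the specific screens again, and 10.6.2 sends even purely mechanical injection-site reactions to the LISR form. On acute allergic injection reactions, which it counts as general allergic events, Section 10.6.2.2 says "A General Allergic Event and/or Local Injection Site Reaction Complementary Form will have to be completed".

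The SAP uses the LISR form in two places. Section 2.4.4.2.5.1 lists "Description of the highest intensity of each symptom recorded in the specific e-CRF page". Section 2.1.4.5.1 builds the local part of a combined allergic grouping from a "selection of PT from the symptoms complementary form for local injection site reaction".

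**The concern.** A site that works from the summary table would complete only the AE page for a non-serious LISR that no other physician sees. The text requires the symptom form for that event. Local tolerability is a named comparison of the two devices up to Week 4 (Protocol Sections 4.2.2 and 9.5): one 2 mL injection against two 1 mL injections. If forms are missing, the symptom profile would rest mainly on the reactions that were referred, while LISR incidence in the same report would count every ticked event. The two displays would then describe different sets of reactions.

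SAP Section 2.5.3 has rules for missing onset date, severity and relationship of an AE, and a general convention that patients with missing data are left out of percentages. It has no rule for an absent symptom form.

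A second, smaller matter is the reporting timeframe for acute hypersensitivity/anaphylaxis, on which Table 9 and the AESI list in Section 10.4.1.3 do not agree.

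**Working it through.** The plan gives no figure to reproduce. The check compares the Table 9 cells with the text and then traces the data source of each SAP reaction output.

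**Step 1. Table 9 against the text**

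| Table 9 row | Safety Complementary Form | Other specific forms | Rule in the text | Result |
|---|---|---|---|---|
| Neither SAE nor AESI | No | No | Form for every reportable LISR and general allergic event (9.2.5, 10.4.1.3, 10.6.1, 10.6.2) | Conflict, however the column headings are read |
| SAE | Yes | No | Same rule | Conflict for a serious LISR or allergic event, unless the first form column is meant to cover it |
| "Acute hypersensitivity/ anaphylaxis" | Yes | No | 10.4.1.3 for all general allergic events; 10.6.2.2 | Same qualified conflict |
| "General allergic event requiring consultation with another physician" | Yes | Yes | Same rule | Consistent |
| LISR with such consultation | Yes | Yes | Same rule | Consistent |

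The two consistent rows mark both columns Yes. This suggests that the table treats the two columns as different forms, and it counts against reading the first column as covering the allergic or LISR form. It does not settle the point for the SAE and anaphylaxis rows. In the first row the question does not arise, because both cells are No.

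**Step 2. Which events are affected**

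An LISR that is non-serious and not referred falls in the first row. Section 10.6.1 exempts isolated redness or swelling under 2.5 cm from AE reporting, unless swelling interferes with activity. The conflict therefore concerns reportable LISRs, not every skin mark.

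**Step 3. Which SAP outputs use the form**

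- LISR incidence: tick box on the AE page (2.1.4.5.1). Form not used.
- General allergic incidence: standardized MedDRA query on coded events (2.1.4.5.1). Form not used.
- Overall LISR intensity, events per injection, time to first LISR (2.4.4.2.5.1): not stated to use the form. Protocol Section 10.4.2 asks the investigator for onset date and intensity for AEs generally.
- Highest intensity of each LISR symptom (2.4.4.2.5.1): form used.
- Local allergic reaction terms in the combined grouping (2.1.4.5.1): form used.
- General allergic event form: no listed analysis is stated to use it.

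Two outputs are therefore exposed. SAP Section 2.4.4.2.5 presents safety by group in the parallel-arm period and overall in the single-arm period, without inferential testing. The by-device part covers the Day 1 dosing, with 33 planned patients per arm.

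**Step 4. How much could be lost**

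Let n be the number of reportable LISRs, r the number referred to another physician, and s the share of the unreferred ones that arise at sites following Table 9. Forms missing = s × (n − r). The documents give none of these values. As an assumption only, take n = 10 and r between 0 and 2:

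- s = 0: 0 × (10 − r) = 0 forms missing.
- s = 1: 10 − 2 = 8 to 10 − 0 = 10 of 10 forms missing.

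The range runs from no loss to almost total loss, and s drives it.

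**Step 5. Timeframes**

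For LISRs, Section 10.4.1.3 and Table 9 agree: 24 hours if another physician is consulted or the event is serious, otherwise routine. For acute hypersensitivity/anaphylaxis, Table 9 has a separate 24-hour AESI row. Section 10.4.1.3 has no such item and makes a general allergic event an AESI only on consultation. A non-serious acute reaction handled without consulting another physician is therefore a 24-hour event under one passage and a routine one under the other. Serious cases are 24-hour under both.

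**The case against.** The best defence is that Table 9 is only a summary and that the protocol says where the detail lies. Sections 9.2.5 and 10.4.1.3 point to Section 10.6 for LISRs and allergic events, and the form rule appears in five sections. To lose data, a site would have to prefer one generic row to several explicit instructions. That is fair as to likelihood: nothing in the documents shows that sites would do so. It does not make the table right. Two sections send sites to it, and the row carries no exception. Nor do the documents say that ticking the LISR box on the AE page opens the form automatically, so that safeguard cannot be assumed.

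A reader might infer that the SAP's by-device reaction analyses as a whole depend on these forms. They do not: LISR incidence and general allergic incidence come from the AE page and coded terms, and only the two outputs in Step 3 draw on the LISR form. A reader might also infer that Table 9 asks for no additional form at all for anaphylaxis or SAEs. It marks the Safety Complementary Form Yes for both, and neither row has a shown effect on an SAP output. Finally, a reader might extend the split timeframe to LISRs. It applies only to non-serious acute hypersensitivity without consultation.

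**Conclusion.** The inconsistency stands, at a minor level. The first row of Table 9 contradicts the form rule for non-AESI LISRs and general allergic events under any reading. The SAE and anaphylaxis rows sit poorly with Sections 10.4.1.3 and 10.6.2.2, but less plainly. The reporting timeframe is split for one narrow class of event.

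The analytical exposure is limited to symptom-level LISR intensity and the local allergic terms. It matters for the device comparison only in the descriptive parallel-arm period. The primary endpoint (product technical complaints) is untouched. The extent of any loss depends on how many sites follow the table and whether the e-CRF prompts for the form; the documents settle neither. The 10-event illustration is an assumption and is not evidence of the size of the loss.

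**What to change.** 1. Add a row or footnote to Table 9: for any LISR or general allergic event, whatever its AESI or SAE status, other specific form Yes. This only restates Sections 9.2.5 and 10.4.1.3.
2. Align the form entry for acute hypersensitivity/anaphylaxis with Section 10.6.2.2.
3. Reconcile Table 9 with the AESI list in Section 10.4.1.3 so that a single timeframe applies to a non-serious acute reaction without consultation. Which one is for the sponsor to decide.
4. Send sites a memo with the corrected table.

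The cost is one corrected table and one memo. The text already refers to the specific e-CRF screens, so no new data collection is needed, and the SAP analyses stay as they are.

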10.4.5 Guidelines for reporting product complaints

Any patient complaint related to the device (SYDNEY or AI)/ injection process must be reported in the Patient complaints form as soon as possible by the Investigator.

Appropriate information in addition to the device (eg, labels or documents like pictures or photocopies) related to product identification and to the potential deficiencies may need to be gathered.

The completed Patient Complaints form and the corresponding device (both elements referred as “complaint sample”) will be sent to the R&D complaint office.

The Investigator will assess whether or not the quality issue has to be reported together with an AE or SAE.

10.5 OBLIGATIONS OF THE SPONSOR

During the course of the study, the Sponsor will report in an expedited manner:

- All SAEs that are both unexpected and at least reasonably related to the IMP (SUSAR), to the regulatory authorities, Independent Ethics Committee (IECs)/Institutional Review Boards (IRBs) as appropriate and to the Investigators.
- All SAEs that are expected and at least reasonably related to the IMPs to the regulatory authorities, according to local regulations.

Adverse events that are considered expected will be specified by the reference safety information (Investigator’s brochure).

The Sponsor will report all safety observations made during the conduct of the trial in the clinical study report.

10.6 SAFETY INSTRUCTIONS

10.6.1 Local tolerability (local injection site reactions)

In case the Investigator or the patient recognizes any signs of local intolerability, then this should be treated and followed-up as per the Investigator’s medical judgment. Specific e-CRF screens are to be filled in. Information on classifying the reaction is provided in [Section 10.4](#), and on reporting these reactions is given in [Appendix G](#).

Local injection site reactions that are related to the alirocumab injection, as opposed to another injectable agent, should be further characterized by evaluating the related symptoms that comprise an injection site reaction such as but not limited to redness, pain, etc. If the patient experiences a local injection site reaction with no signs or symptoms except for erythema/redness, and/or swelling, and the diameter of the erythema/ redness, or swelling measure <2.5 cm, no AE for local injection site reaction needs to be reported as this is not typically considered a clinically important finding. However, if the patient has a reaction of swelling with a diameter <2.5 cm that interferes with activity, then it should be considered as a clinically relevant finding and should be reported as an AE with a corresponding grade of moderate or severe, in accordance with [Appendix G](#).

